8.4 Adverse Events and Serious Adverse Events

A serious adverse event (SAE) in this trial is defined according to the following severity grades:

- Grade 1: Mild discomfort, not interrupting normal activities
- Grade 2: Moderate discomfort, interrupts normal activities but not incapacitating
- Grade 3: Severe, resulting in disability or necessitating medical consultation (SAE)
- Grade 4: Requires hospitalization (SAE)
- Grade 5: Results in death (SAE)

Only events classified as Grade 3, 4, or 5 are considered SAEs within the context of this trial

- Time Period and Frequency for Collecting SAE Information
 - Time period
 - Start: Apr 15, 2024
 - End: Oct 15, 2025
 - Frequency
 - SAEs will be documented as they are reported by participants.
- Recording of SAEs

- While prior studies suggest minimal evidence of SAEs resulting from exercise, diet, or meditation in cancer survivors, all SAEs encountered during this trial will be meticulously recorded. Participants can report SAEs directly via the app, or coaches may report on their behalf. Reports should include the severity grade, description of the event, and the participant's perspective on whether the SAE was related to trial interventions..
- Follow up of SAEs
 - All participants will continue receiving standard care from their healthcare providers. In the event of an SAE, a dedicated physician will be assigned to assess the situation, provide immediate recommendations, and categorize the cause of the SAE based on discussions with the participant. This classification will also be documented.
- Regulatory Reporting Requirements for SAEs
 - SAEs must be reported to the Institutional Review Board (IRB) within 24 hours of the event's identification. Additionally, the Sponsor will ensure prompt notification of all investigators regarding any SAEs, enabling them to inform participants about potential risks and take any necessary precautions.
- The grading of adverse events is aligned with the Common Toxicity Criteria for Adverse Events (CTCAE) standards, which detail adverse events on a scale from 1 to 5. The complete CTCAE documentation is available on the National Cancer Institute's website: [NCI CTCAE Information](#).

Section 9: STATISTICAL CONSIDERATIONS

The analysis will be conducted on all participant data at the end of 3 months, 6 months, 12 months and 18 months (ie. end of the trial).

9.1 Analysis Sets

- The analysis will include the following datasets:

- Intent-to-Treat (ITT) set: Including all randomized survivors, regardless of their adherence with the entry criteria. This set will be used for the primary analysis of healthcare expenditure reduction and cancer progression.
- Per-Protocol (PP) set: Including participants who completed the trial according to the protocol without significant deviations. PP set is a subset of ITT set, excluding survivors with major protocol deviations or those who do not complete the trial. This set will be used to summarize efficacy and support sensitivity analyses.

9.2 Analyses Supporting Primary Objective(s)

- The primary analysis will focus on quantifying the impact on total healthcare expenditure including hospitalization costs, medication expenses, outpatient visits, and any other related healthcare services over the trial period.
- We will try to establish the efficacy of Complement Theory by measuring the difference in mean total healthcare expenditure between the intervention and control groups at 3, 6, and 12 months and 18 months from baseline.
- **Statistical Model, Hypothesis, and Method of Analysis**
 - Primary Estimand (Healthcare Expenditure Reduction):
 - Null Hypothesis (H0): There is no difference in healthcare expenditure between participants in the Complement Theory program and those in the control group.
 - Alternative Hypothesis (H1): Participants in the Complement Theory program exhibit a significant reduction in healthcare expenditure compared to the control group.
 - Baseline Data Analysis: Baseline demographics and characteristics will be provided and summarized in both treatment and control groups. Standardized mean differences (SMDs) will be calculated as the measure of distance between groups. SMDs of 0.2 to <0.5, 0.5 to <0.8 and ≥ 0.8 are considered small, medium, and large, respectively. Frequencies and percentage will be provided for the binary variables as well as the

categorical variables (Yes/No); mean (standard deviation) and median (range) will be computed for continuous variables.

- Method of Analysis: A Generalized Linear Model (GLM) with an appropriate link function and distribution family that best fits the distribution of healthcare expenditure data. Both univariate and multivariate analyses will be conducted. The method will capture the effect on the outcome in treatment and control group from each independent variable. In addition, the strength of the effect from each of the variables would be evaluated through the statistical test significance, i.e., P value, at 95% confidence interval.
- **Handling of Intercurrent Events of Primary Estimand(s)**
 - For participants who discontinue the intervention or are non-adherent, we will employ a treatment policy strategy. This means all data collected will be analyzed as per the initial treatment assignment, regardless of the discontinuation or level of adherence, preserving the intention-to-treat principle.
- **Handling of Missing Data**
 - Participants will be eligible for analysis if they have contributed a minimum amount of baseline data. The primary analyses will be based on cases with complete data. Then, multiple methods will be used to compensate for missing values in the analytical dataset.
 - An imputation rule will be assessed in such a way that if a variable has a percentage of missing values higher than a certain threshold (i.e., 50%, 70%, or 80%), then no imputation will be conducted for this variable and it may be dropped from the analytical sample to avoid an inaccurate result.
 - For intermittent missing data points, we may use LOCF, where a participant's last observed data point is carried forward to replace missing future observations.

- Multiple Imputation: For more systematically missing data, multivariate imputation by chained equation (MICE) will be used, i.e., filling the missing data multiple times based on the effect from other covariates by constructing a multivariate regression model. Multiple Imputation (MI) is superior to single imputation, as it measures the uncertainty of the missing values in a better way. The number of imputations will be 10, i.e., 10 datasets with imputed data will be created. Each imputed data set gives a point estimate of the regression coefficients as well as its standard deviation, which will be combined across the 10 datasets to obtain the final estimate of the causal RR/HR and their 95% CIs. The chained equations approach is also very flexible and can handle different variables of different data types as well as complexities such as bounds, or survey skip patterns.
- **Sensitivity Analysis**
 - To complement our intention-to-treat (ITT) analysis, a per-protocol analysis will be performed, including only participants who fully adhered to the intervention, to explore the effect of adherence on healthcare expenditure reduction.
- **Supplementary Analysis**
 - Efficacy Analysis: survivors in the treatment and control group will be compared for the outcome variables. The comparison will be evaluated based on both SMD and P value. SMD greater than 0.2 will be considered as acceptable differences (section 3.3 indicated the definition of SMD). Descriptive statistics will be compared between treatment groups and control groups, and P values will be calculated using ANOVA tests comparing means of continuous variables, Brown-Mood test to compare the medians, and Chi-Square tests for binary and categorical variables. The differences will be considered as statistically significant within 95% confidence interval, i.e., P value less than 0.05.

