5.3 Inclusion Criteria

- Cancer Type : Breast, Prostate, Colorectal, Lung and Other Cancers
 - Other Cancers here refers all other cancer types apart from Breast, Prostate, Colorectal and Lung Cancer
- Cancer Stage: Stage 1 to 4
- Treatment Status: Has undergone any cancer-related treatment in last 12 months
- Age : 21 to 64
- Permission to access to last 1 year digital health records
- Access to smartphone or a tablet

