8.2 Efficacy Assessments and Procedures

Healthcare Expenditure Reduction (Trial Objective 1):

- Endpoint: Total healthcare expenditure, including hospitalization costs, medication expenses, outpatient visits, etc.
- Assessment Procedure: Conduct comprehensive assessments of healthcare expenditure for participants in both the intervention and control groups at specified time points (e.g., baseline, 3 months, 6 months, 12 months and 18 months).
- Data Collection: Obtain detailed data on healthcare utilization, costs of medical services, medication expenses, and related healthcare expenditures through EHR access granted by participants, and participant-reported information.
- Analysis: Calculate the mean total healthcare expenditure for each group and compare the differences between the intervention and control groups over the trial period.

Impact on Adherence to Treatment (Trial Objective 2):

- Endpoints: Change in MMAS-8 scores
- Assessment Procedures: Administer the MMAS-8 questionnaire to assess adherence levels to treatment regimen at baseline and specified time points during and after the intervention period.
- Data Collection: Obtain self-reported scores from participants on adherence levels.
- Analysis: Calculate the mean difference in change in survey scores between the intervention and control groups at each time point to evaluate the impact

Improvement in Quality of Life Score (QoLS), Pain, Sleep and physical activity (Trial Objective 3):

- Endpoint: Change in FACT-G, GLTEQ, BPI-ShortForm, PROMIS scores measuring quality of life, physical activity, pain levels, and sleep
- Assessment Procedures: Administer the above four questionnaires to assess participants' at baseline and specified time points during and after the intervention period.
- Data Collection: Obtain self-reported scores from participants on Quality of Life, Pain levels, and behavior change specifically with Healthy Diet intake and ability to do physical activity.
- Analysis: Calculate the mean difference in change in scores between the intervention and control groups at each time point to evaluate the impact of the intervention.

Reduction in Employee Absenteeism (Trial Objective 4):

- Endpoint: Number of leave days taken by employed cancer survivors due to health issues.
- Assessment Procedures: Track the number of leave days (sick leave, short-term disability, long-term disability) taken by participants in both groups throughout the trial period.

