9.7 Sample Size Determination

- The metric-wise sample size calculation is provided in the table below on alpha as 0.05 and power of 80% for the one-tail test at enrollment ratio = 1.

- While we are conducting the power analysis and sample size calculation based on several variables (outcomes) of interest, the sample size was computed separately for each parameter in the study and the greatest is used to obtain sample size.
- The analysis (detailed below in table) showed that sample of size of 102 is powerful enough for the analysis to cover 100% of primary and secondary metrics.
- Now since we believe that the long follow-up duration of 12 months for our trial will lead to around 30% drop-offs, we decided a final sample size of 146 (73 control, 73 test).
- So even if get 30% or 44 participants drop off we end up with final sample set of 102 (51 control, 51 test) and would be able to come to statistically significant effects ($p < 0.05$) with respect to 100% of primary and secondary metrics.

Metric Segment	Sub Metric	Control Data	Test Data	Assumed Variance	Sample Size
Primary Outcome / Concerns					
Medical Expenditure	Total Healthcare Expenditure (Planned + Unplanned)	10000	8000	Variance of 4000	102 (51 Control, 51 Test)
	No of Urgent Care Visits	3	2.5	Variance of 0.5	28 (14 Control, 14 Test)
	No of ED Visits	5	3.45	Variance of 0.8	10 (5 Control, 5 Test)
	No of unplanned outpatient/office	4.28	3.5	Variance of 0.8	28 (14 Control, 14 Test)

	visits (other than ED)				
	Unplanned Hospitalisations	5	4	Variance of 0.8	18 (9 Control, 9 Test)
	Length of hospital stay	3	2	Variance of 0.8	18 (9 Control, 9 Test)
	No of planned outpatient visits	2	1.8	Variance of 0.3	58 (29 Control, 29 Test)
	No of planned hospital visits	1.25	1	Variance of 0.1	10 (5 Control, 5 Test)
	Length of hospital stay	3	2	Variance of 0.8	18 (9 Control, 9 Test)
	Total Prescription Medicine Expenditure	1000	950	Variance of 80	80 (40 Control, 40 Test)
Secondary Outcome / Concerns					
Adherence	MMAS scale	4.5	7	Variance of 2.5	28 (14 Control, 14 Test)
QoLS Score, Pain Levels, Sleep Quality, Physical Activity	QoLS Score (FACT-G)	70	85	Variance of 20	42 (21 Control, 21 Test)
	Brief Pain Inventory (Short Form)	80	60	Variance of 35	78 (39 Control, 39 Test)

	PROMIS (Short Form)	70	55	20	46 (23 Control, 23 Test)
	GLTEQ	25	17	10	42 (21 Control, 21 Test)
	Calorie Burnt	120	198	Variance of 70	22 (11 Control, 11 Test)
Presenteeism	Attitude towards work	2	4	Variance of 1.5	16 (8 Control, 8 Test)

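### The primary expenditure model does not pre-specify baseline expenditure as a covariate, or say whether the adjusted result is primary, although baseline cost is due to be collected

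*Combined protocol and SAP*

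**What the plan says.** All references are to the Combined protocol and SAP unless stated.

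- **Model.** Section 9.2 gives the primary method as "A Generalized Linear Model (GLM) with an appropriate link function and distribution family that best fits the distribution of healthcare expenditure data". It adds that univariate and multivariate analyses will both be run and that the effect of each independent variable will be captured. It does not list those variables or rank the two analyses. Baseline or prior expenditure is not named as a model term anywhere in section 9.
- **Other comparisons of the same outcome.** Section 8.2 calculates mean expenditure per group and compares the groups. The supplementary analysis in 9.2 uses ANOVA, Brown-Mood and chi-square tests. None of these mentions adjustment.
- **Baseline cost data.** Section 8.2 places expenditure assessments "at specified time points (e.g., baseline, 3 months, 6 months, 12 months and 18 months"). Section 6.1 schedules claims access at baseline in both arms. Section 5.3 has the entry criterion "Permission to access to last 1 year digital health records".
- **Missing data.** Section 9.2 bases the primary analyses on complete cases, then adds other methods.
- **Randomisation.** Section 6.6 makes allocation depend on cancer type only.
- **Sample size.** Section 9.7 uses "alpha as 0.05 and power of 80% for the one-tail test at enrollment ratio = 1". The expenditure row reads "Total Healthcare Expenditure (Planned + Unplanned) 10000 8000" with "Variance of 4000", giving 51 per arm.
- **Estimand.** Section 3 defines it as the difference in mean total expenditure between the arms.

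**The concern.** A participant's cost before randomisation is a natural candidate to predict cost afterwards. Eligibility covers stages 1 to 4 and every cancer type, and neither stage nor prior cost is balanced by the randomisation. If baseline cost stays out of the model, whatever part of the outcome variance it explains remains in the error term. The interval is then wider than it needs to be, and a chance imbalance is reported (9.2 tabulates baseline standardised mean differences) with no stated step to correct for it.

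There is a second problem. With an open covariate list and two unranked analyses, the team could choose between an unadjusted result and several adjusted ones after seeing the data. For a primary endpoint that choice should be closed in advance.

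**Working it through.** **1. Reproduce the plan's figure.** Inputs from section 9.7: difference 10000 − 8000 = 2000; spread 4000; one-tailed alpha 0.05; power 80%; allocation 1:1.

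- Reading 4000 as a standard deviation: d = 2000/4000 = 0.5. The one-tailed two-sample t-test needs 50.15 per arm, rounded up to 51, so 102 in total. This matches "102 (51 control, 51 test").
- Dropout: 102/(1 − 0.30) = 145.7, so 146, as stated.
- Reading 4000 literally as a variance (standard deviation √4000 ≈ 63) gives 1 per arm, which does not reproduce the figure. A two-sided normal-approximation calculation gives 126, which does not either.

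The planned size is therefore an unadjusted two-mean comparison with no credit for baseline information.

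**2. Effect of adjustment.** In a linear model, adjusting for a covariate with correlation r to the outcome multiplies the residual variance by 1 − r². The effective standard deviation is 4000 × √(1 − r²), and the effective d is 0.5/√(1 − r²). The documents give no r, so the values below are assumptions. Power uses the non-central t at 51 per arm. The 95% half-width is 1.96 × SD × √(2/51).

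| Assumed r | Variance removed | Effective SD | One-tailed power | Two-sided power | 95% half-width |
|---|---|---|---|---|---|
| 0 (unadjusted) | 0% | 4000 | 80.6% | 70.6% | 1553 |
| 0.2 | 4% | 3919 | 82.0% | 72.3% | 1521 |
| 0.3 | 9% | 3816 | 83.7% | 74.6% | 1481 |
| 0.5 | 25% | 3464 | 89.4% | 82.3% | 1345 |
| 0.7 | 49% | 2857 | 96.9% | 93.8% | 1109 |

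**3. Chance imbalance.** At 51 per arm the standard error of a baseline standardised difference is √(2/51) = 0.198. The probability of a difference of at least 0.2 in either direction is 2 × P(Z > 0.2/0.198), about 31%. If r = 0.5, an imbalance of 0.2 shifts the unadjusted difference by 0.2 × 0.5 × 4000 = 400, which is 20% of the planned 2000.

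**4. What complete-case analysis could take back.** If participants without a baseline cost drop out of the adjusted model, the gain can vanish. With r = 0.3 and 46 per arm (about 10% lost), one-tailed power is 80.2%. With r = 0.5 and 38 per arm (about 25% lost), it is also 80.2%. These loss rates are assumptions, but they show that the covariate needs its own missing-data rule.

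**The case against.** A reader might infer that the model excludes prior expenditure, so that the baseline data go unused. The text does not support that. Section 9.2 promises multivariate analyses with unnamed variables, and baseline cost could be one of them. The supportable statement is that it is not pre-specified and that the primary result is not identified.

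A reader might also infer that a full prior year of cost is guaranteed and adjustment is therefore free. That goes too far as well. The entry criterion concerns permission to access health records. Section 8 says participants will be asked to provide claims and explanation-of-benefits documents. Section 11.2 recommends access for 6 to 18 months, without saying that the period lies before baseline. Some participants may have a short or incomplete cost history, and under the complete-case rule they could be lost from the adjusted model (step 4). This objection stands, and the fix has to deal with it.

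The gain itself is conditional. No correlation is given; at 0.1, one-tailed power would be 80.9%, a negligible change. Everyone enrolled had cancer treatment in the previous 12 months, so past cost may reflect a completed episode and predict later cost only weakly. The 1 − r² factor is a linear-model result and only approximate for skewed costs in a GLM whose link and family are still open.

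Finally, under randomisation the unadjusted comparison is unbiased in expectation, and the stated sample size reproduces. Adjustment improves efficiency; it does not repair an error. That is correct and limits the weight of the point, but it does not justify leaving the primary model's covariates open.

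**Conclusion.** The point holds as a gap in pre-specification. In the Combined protocol and SAP, the primary expenditure GLM does not name baseline expenditure as a covariate or say whether the univariate or multivariate result is primary. The accompanying comparisons are unadjusted, although baseline expenditure and claims are scheduled for collection.

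The size of the loss cannot be derived from the documents. On the plan's own inputs, with 4000 read as a standard deviation, one-tailed power at 51 per arm would rise from 80.6% by about 1 percentage point at an assumed correlation of 0.2, 3 at 0.3, 9 at 0.5 and 16 at 0.7. The benefit is minor at low correlation and substantial from about 0.5. It depends on keeping participants with incomplete baseline cost in the model. The planned 102 and 146 are not invalidated.

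The point is confined to the Combined document. In the other Protocol, expenditure is exploratory and section 9 gives no model for it.

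**What to change.** Amend section 9.2 of the Combined protocol and SAP as follows.

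1. Name total expenditure before randomisation as a covariate, over a fixed look-back window that the claims actually obtained can support. State its form, for example log-transformed with an indicator for zero cost. Include cancer type, the randomisation factor.
2. Declare this adjusted model primary and the unadjusted comparison supportive.
3. Keep participants with missing baseline cost in the model, by baseline imputation or a missing-data indicator, and state that the complete-case rule does not remove them for this reason.
4. Obtain the adjusted difference in mean expenditure by marginal standardisation: predict each participant's cost under both arms, average over the sample, and subtract. The result matches the section 3 estimand whichever link is used. It is not the standardised mean difference that 9.2 uses elsewhere.

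The planned sample size can stay, with any gain treated as a margin, since the correlation is unknown. The cost is a short SAP edit plus modest work to build the baseline cost variable and handle incomplete records. No extra participants, visits or types of data are needed.

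### Combined protocol and SAP: the primary expenditure analysis is assigned to all randomised participants but then based on complete cases, and the imputation that follows has no stated role

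*Combined protocol and SAP*

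**What the plan says.** All references are to the combined protocol and SAP unless stated. Total healthcare expenditure is its primary endpoint, and the estimand in section 3 is a difference in mean expenditure between arms.

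- **Section 9.1** defines the set: "Intent-to-Treat (ITT) set: Including all randomized survivors, regardless of their adherence with the entry criteria". It also gives the set its use: "This set will be used for the primary analysis of healthcare expenditure reduction and cancer progression". The per-protocol set leaves out people who do not finish the trial.
- **Section 9.2, intercurrent events,** adopts a treatment-policy strategy: whatever data are collected after discontinuation or non-adherence are analysed by assigned arm.
- **Section 9.2, missing data,** opens with an entry condition, "Participants will be eligible for analysis if they have contributed a minimum amount of baseline data", and does not define the minimum. Next comes "The primary analyses will be based on cases with complete data", and after it "Then, multiple methods will be used to compensate for missing values in the analytical dataset". The methods listed are LOCF ("For intermittent missing data points, we may use LOCF") and chained-equations imputation with 10 datasets, pooled to a risk or hazard ratio.
- **Section 9.2, sensitivity analysis,** names only the per-protocol analysis.
- **Section 9.7** expects that the long follow-up "will lead to around 30% drop-offs", that is 44 of 146 participants, leaving 102.

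In the separate Protocol, FACT-G is primary and has multiple imputation (9.2). Expenditure is exploratory there and has no missing-data rule.

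**The concern.** An analysis of everyone randomised and an analysis restricted to complete cases are different analyses once data are missing, and this plan expects substantial loss. A complete-case analysis also discards the costs already recorded for people who leave part-way, although the treatment-policy text says collected data will be used. The one named sensitivity analysis excludes non-completers too, so it cannot show whether their absence matters.

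The plan gives reasons why loss might relate to cost and might differ by arm. Under 7.1, disease progression can end the intervention, and continued follow-up afterwards is not assured. Failure to follow the live-coaching instructions is a ground for discontinuation, and only the test arm has live coaching. Claims and health-record data come through the participants (sections 8 and 11.2), so a person who leaves may take the cost data along. None of this shows that such a pattern will occur. It shows that the plan cannot rule it out.

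At stake is whether an observed saving reflects the programme or reflects who remained. Leaving the primary estimator unnamed also allows it to be chosen after the results are seen.

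**Working it through.** **1. The plan's own figures.** Inputs from 9.7: means 10,000 and 8,000 (difference 2,000), spread 4,000, one-sided alpha 0.05, power 80%, 1:1 allocation. The table labels 4,000 a variance, but it reproduces the stated size only if read as an SD.
- Normal approximation: n = 2 × (1.645 + 0.842)² × (4,000 / 2,000)² ≈ 49.5, so 50 per arm.
- One-sided t-test: 50.15, so 51 per arm, 102 in total, as stated.
- Inflation: 102 / 0.70 = 145.7, so 146. Loss: 146 × 0.30 = 43.8, about 44. Left: 146 − 44 = 102.

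**2. Bias formula.** Let d be the share of an arm that drops out and G the dropouts' mean cost minus the completers' mean cost. The full-arm mean equals the completers' mean plus d × G, so the completers' mean equals the full-arm mean minus d × G. With no true effect:

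apparent saving = d_test × G_test − d_control × G_control

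**3. Cost-related dropout in the test arm only (G_control = 0).** The documents give no value for G, so a range is used. At d = 0.30 in each arm, completers per arm are 73 × 0.70 = 51.1 and SE = 4,000 × √(2 / 51.1) ≈ 791. The rejection rate is Φ(saving / 791 − 1.645).

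| Assumed G | False saving, 0.30 × G | One-sided rejection at nominal 5% |
|---|---|---|
| $1,000 | $300 | 10% |
| $2,000 | $600 | 19% |
| $4,000 | $1,200 | 45% |

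A false saving as large as the planned $2,000 would need G = 2,000 / 0.30 ≈ $6,667. At 20% dropout it would need $10,000, and at 40% it would need $5,000.

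A simulation with gamma-distributed costs (mean 10,000, SD 4,000, 30% dropout per arm) agrees. G of about 2,005 gave a bias of 600 and 18% rejection; G of about 3,588 gave 1,085 and 44%. Random dropout gave no bias and about 5% rejection.

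**4. Selective dropout in both arms with the same G.** The saving becomes (d_test − d_control) × G.
- 30% and 30%: 0, whatever G is.
- 35% test, 25% control: 0.10 × G, or $200 to $400 for G = $2,000 to $4,000.
- 40% test, 20% control: 0.20 × G, or $400 to $800.

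With more selective loss in the control arm the sign reverses, and a real saving would be understated.

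**5. Dependence on the control arm in a two-group example.** Assume that 30% of each arm cost $16,000 and that the overall mean is $10,000. The others then average (10,000 − 0.30 × 16,000) / 0.70 = $7,429. In the test arm let 60% of the high-cost group drop out, with 30% loss overall. The retained mean is (0.12 × 16,000 + 0.58 × 7,429) / 0.70 ≈ $8,898.
- Random control dropout: 10,000 − 8,898 ≈ $1,100 false saving.
- 40% control high-cost dropout: (0.18 × 16,000 + 0.52 × 7,429) / 0.70 ≈ $9,633, a false saving of about $735.
- 50%: (0.15 × 16,000 + 0.55 × 7,429) / 0.70 ≈ $9,265, about $367.
- 60%: the same as the test arm, so zero.

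**The case against.** The strongest reply is that imputation is already planned. The complete-case sentence is followed at once by "Then, multiple methods will be used to compensate for missing values in the analytical dataset", the text calls multiple imputation superior to single imputation, and the pooled result is described as final. On that reading the section is one sequence that ends in imputation. A reader might infer the opposite, that the plan simply drops everyone with incomplete data. The documents do not establish that either. What stands is that "The primary analyses will be based on cases with complete data" is the only sentence that says what the primary analyses rest on, and nothing gives the later methods a role.

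Further points have force:

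- Treatment policy governs intercurrent events. It does not say how uncollected data are handled, so the conflict rests mainly on 9.1 and, through 9.2, on the discarded partial data.
- The 44 is a drop-off assumption, not a documented count of incomplete cost records. Expenditure is analysed at 3, 6, 12 and 18 months, so early losses may be smaller. Records access of 6 to 18 months (11.2) could make late losses larger.
- A reader might infer lost power. The 102 already allows for 30% loss, so planned power is unaffected.
- Standard multiple imputation removes cost-related bias only if the observed data explain the dropout. It does not cure every scenario above.

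**Conclusion.** The point holds for the combined protocol and SAP. Its analysis set and its complete-case sentence conflict, and the primary estimator for expenditure is not settled. If the 30% drop-off applies to cost data, a complete-case analysis omits about 44 of 146 participants.

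The bias is possible, not shown. With loss related to cost only in the test arm, false savings run from $300 to $1,200 for cost gaps of $1,000 to $4,000. They fall to zero when selective loss is equal in both arms and change sign in the reverse pattern. These figures rest on assumed gaps and assumed dropout by arm, and on reading 4,000 as an SD.

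A reader might go further and infer that sicker, costlier participants will leave and so produce apparent savings. No passage gives a relation between dropout and cost, and none gives dropout by arm. Nor does the point reach the Protocol's primary result: FACT-G is primary there with multiple imputation, and the gap concerns an exploratory endpoint. This is a change that should be made, not evidence that the result would be wrong.

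**What to change.** In section 9.2 of the combined protocol and SAP:

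1. Name one primary expenditure estimator: multiple imputation by arm, on all randomised participants, using the partial cost data of those who leave early.
2. Pool the difference in mean cost, which is the estimand, in place of a risk or hazard ratio.
3. Move the complete-case analysis to the sensitivity analyses.
4. Drop LOCF for costs. Carrying a cumulative total forward adds no later cost, and carrying an interval cost forward assumes a constant rate.
5. Add a delta-adjusted sensitivity analysis for data missing not at random, in which imputed costs are shifted by a stated range in each arm separately.
6. Remove the undefined baseline-data condition from the primary analysis, or reconcile it with 9.1.

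Carry the same rule into the Protocol for its exploratory expenditure analysis.

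The cost is a wording change and slightly more analysis work. Chained-equations imputation is already planned, and no new data collection is needed.
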